5.3 OUTCOME MEASURES

QUANTATIVE OUTCOMES

Lifestyle behaviour of participants will be assessed at baseline and 6 months, 12 months and 2.5 years after completion of the Online MS course (intervention or standard-care). Lifestyle/behaviour outcomes to be measured include:

a. Exercise

To assess physical activity we will use The International Physical Activity Questionnaire - Short Form (IPAQ-SF), a 7-item 7-day recall of frequency and duration of vigorous and moderate physical activity, walking, and sitting assessed in nine items (Craig et al., 2003). The IPAQ and its short form have been validated in several studies and populations globally, and the long form has been used previously for people with MS (Stroud, Minahan, & Sabapathy, 2009; Weikert et al., 2012).

b. Diet

Since we aim to assess diet broadly with a particular consideration for fats, we will modify the Diet Habits Questionnaire (DHQ) (McKellar et al., 2008). The original 24-item DHQ has eight dietary sub-scores, and assesses saturated and unsaturated fat intake, fruit and vegetable, fibre, takeaway, snack habits, and omega-3 consumption, among other estimates. In our modified version, we removed three items regarding sodium intake, and one item on alcohol was replaced with an alternate alcohol assessment measure. We added a researcher-devised item regarding oily fish consumption that was separate from the DHQ: "How often do you eat oily fish such as sardines, mackerel, herring, salmon, tuna or trout? (Never; Less than once a week; About 1 - 2 times a week; About 3 - 4 times a week; At least 5 times a week) and options regarding "I don't eat meat" and "I don't eat dairy".

c. Alcohol consumption

Volume and frequency of alcohol consumed will be queried. In Australia a standard drink is considered to be 10 grams of ethanol. Frequency of binge drinking, defined by the Australian Bureau of Statistics as more than 7 drinks a week for men, and more than 5 for women, will be queried.

d. Smoking

Smoking status (never/ex-smoker/current smoker) will be queried. For current smokers, typical number of cigarettes per week will be queried along with the total years they have been smoking. For ex-smokers, their typical number of cigarettes per week when they smoked will be queried, as well as the total years they smoked and the duration since they quit smoking.

e. Omega-3 uptake

We will assess both the type and daily dosage of omega-3 supplementation used on average in the last 12 months. Types of omega-3 will include fish oil, high potency fish oil, and flaxseed oil.

f. Vitamin D uptake

We will assess vitamin D supplementation by measuring dosage and frequency of vitamin D intake.

g. Sun exposure

To assess sun exposure we will modify the Ausimmune Longitudinal Study in people with MS (Lucas et al, Neurology, 2011). For each of summer and winter, participants will be asked to report number of days per week they were out in the sun; average duration spent in the sun on days they were out in the sun (none, 1-15 minutes to >60 minutes). We will also query whether participants deliberately increased their sun exposure to increase their vitamin D levels.

h. Stress management

We will use 2 questions of the Mindfulness Adherence Questionnaire (MAQ)(Hassed et al., 2021), a 6-item subset of main questionnaire, to measure the type and frequency of the participant's experience of meditation.

Other measures:

a. Sociodemographics

Data will be collected for date of birth, sex, current location of residence, country of birth, cultural background (Australian Standard Classification of Cultural and Ethnic Groups(Statistics, 2012)) and highest education level completed at baseline only, whereas marital status and employment status will be queried at all timepoints.

b. Medication use

Participants will also be asked to indicate whether they take prescription antidepressant, anxiolytic/sedative, or antifatigue medications.

c. Comorbidities

The Self-administered Comorbidity Questionnaire (SCQ) will be used to assess the presence of comorbidities in the absence of medical record review (Sangha, Stucki, Liang, Fossel, & Katz, 2003). It has demonstrated criterion validity when assessed against medical records (Stolwijk et al., 2014), and has been used in studies of participants with MS (Giovannetti et al., 2016; Holper et al., 2010). The clinically meaningful difference in the number of comorbidities for MS assessed using the self-administered comorbidity questionnaire has not been determined.

d. BMI

Body Mass Index (weight/height)² will be calculated from data collected on self-reported participant weight and height and classified using the WHO classification system (Organization, 2017). A meaningful change in BMI is difficult to will be defined by comparing to BMI at baseline.

e. Perceived Social Support

The 12-item multidimensional Scale of Perceived Social Support (MSPSS) will be used to measure participants' social interaction and satisfaction with social support (Zimet, Dahlem, Zimet, & Farley, 1988). Higher score of MSPSS indicates higher quality of social support.

Health outcomes of participants will be assessed at baseline and 6, 12 and 30 months after completion of the respective Online MS course. Health outcomes measured include:

f. Mental and physical quality of life (qol)

The MSQOL-54 will be used to assess a spectrum of HRQOL outcomes. In particular, the two primary outcome measures for this study will be change in Physical Health Composite (PHC) and Mental Health Composite (MHC) derived from the MSQOL-54. PHC and MHC are derived by combining scores of relevant subscales (Vickrey, Hays, Harooni, Myers, & Ellison, 1995). Although minimal clinically important differences have not been established for the MSQOL-54 composite scores, differences of at least five points have previously been determined as the minimum clinically meaningful change in an HRQOL measure (Osoba et al., 1998; Taphoorn, et al., 2005). This is based on recommendations that a difference

equivalent to half the standard deviation be universally considered an important magnitude for all HRQOL tools (Norman, Sloan, & Wyrwich, 2003). The MSQOL-54 has been psychometrically validated since 1995, used online and also translated into many different languages.

g. Fatigue

Clinically significant fatigue will be measured by the 9-item Fatigue Severity Scale (FSS) (Krupp, LaRocca, Muir-Nash, & Steinberg, 1989). The FSS has good internal consistency, stability, and sensitivity to change over time (Amato et al., 2001; Smedal et al., 2011). A mean score ≥ 4 has been suggested as a cut-off to indicate clinically significant fatigue and is widely used for people with MS (Lerdal, Celius, & Moum, 2003; Marrie et al., 2005; Smedal et al., 2011). A meaningful change on the FSS has been reported demonstrated to be a change of ≥ 1.9 points in people with MS (Learmonth et al., 2013) and so here a change in mean score of 1.9 points or more will be considered clinically meaningful.

h. Anxiety and depression

The Hospital Anxiety and Depression Scale (HADS) for the presence of and severity of anxiety and depressive symptoms. The HADS is commonly used for screening for anxiety and depression, as well as selecting and monitoring treatment and has been used to measure depression in MS (Zigmond & Snaith, 1983).

i. Patient-reported disability

The Patient-Determined Disease Steps (PDDS) is a self-reported measure of ambulatory disability. The PDDS is scored ordinally from 0 (normal) to 8 (bed bound) with detailed descriptors and definitions. It correlates well with the EDSS and moderately with the widely used Multiple Sclerosis Functional Composite and has excellent test-retest reliability. PDDS is considered a practical tool to use to assess changes in disability over time (Hohol, Orav, & Weiner, 1999). One step will be considered a clinically meaningful change in the PDDS.

j. Self-efficacy

Self-efficacy (the belief in one's ability to produce the effects or outcomes one wants) will be measured using the University of Washington Self-Efficacy (UWSE) survey, a psychometrically sound instrument that includes 6 items for measuring self-efficacy, validated in MS (Amtmann et al., 2012).

Primary intervention quantitative outcomes/endpoints:

The two primary outcome measures for this study are changes (improvements) from baseline in 1. Physical Health Composite (PHC) and 2. Mental Health Composite (MHC) derived from the MSQOL-54 in the short-term and medium-term. Differences of at least five points have previously been determined as the minimum clinically meaningful change in an HRQOL measure (Osoba, Rodrigues, Myles, Zee, & Pater, 1998; Taphoorn & Bottomley, 2005). Previous data suggests a difference of five points is achievable in a sample of people with MS (Hadgkiss, Jelinek, Taylor, et al., 2015).

Secondary intervention quantitative outcomes/endpoints:

Secondary outcomes include clinically relevant changes (improvements) in depression, anxiety fatigue, disability and self-efficacy in the short-term and medium-term.

QUALITATIVE OUTCOMES

A qualitative study using semi-structured interviews will be conducted within one month and 12 months after completing the MS Online course (the same group of people with MS will be interviewed at both time points).

A randomly selected sample of approximately 15 participants from each the standard-care course arm and intervention course arm will receive an email or phone call requesting their participation in 30 to 60 minutes qualitative interview. Interviews will be conducted by telephone or via the internet by 3 trained interviewers. All interviewers will be involved in the first three interviews to ensure consistency in the format and content of qualitative interviews.

Semi-structured interviews have been developed based on an iterative process by researchers. *Schedules of qualitative interviews are described in the attached file, MSOC RCT qualitative interviews schedule.docx*

The 1-month interview guide will cover the following domains:

- 1) Participants' views regarding motivation to undertake the course
- 2) Views of the content of the course
- 3) Participants' experiences
- 4) Use of community
- 5) Initial changes to lifestyle
- 6) Initial changes to attitudes to MS, health and the future

The 12-month interview will cover the following domains:

- 1) Adoption of lifestyle recommendations
- 2) Perceived health
- 3) Sense of community and support
- 4) Attitude to MS, health and the future

Interviews will be digitally recorded and transcribed by voice recognition software. All recordings and transcribed files will be securely stored in a re-identifiable format.

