Evidence behind a dietary influence on MS disease activity and QOL: evidence on saturated fat, and evidence regarding diet and its relationships with MS onset and progression. Introduction to dietary plan and benefits of different food groups.

Session 3: Sunlight and vitamin D

Detailed background information about how vitamin D is made from the action of sunlight is presented, along with evidence supporting a role of vitamin D in MS disease activity. Recommendations for optimal levels of supplementation and blood levels are presented.

Session 4: Physical activity/Exercise

The benefits of exercise are explained for people with MS (neurological, cognitive, physical), how and why. In addition, evidence regarding the benefits of exercise will be presented. How to implement an exercise plan with video examples provided.

Session 5: Stress and stress reduction

Introduction to mental health and relevance in MS. Participants are introduced to the science behind stress and its link to inflammation/MS. Mind-body connection, meditation and other stress reduction techniques to supplement the practical sessions on meditation they receive throughout the program. How to develop a mental health and wellbeing improvement strategy.

Session 6: Family primary prevention

Participants are introduced to the issue of primary prevention of MS in close family members who are at increased risk of developing the disease, and strategies for reducing this risk. This session will cover risks associated with smoking and excessive alcohol intake and MS progression.

Session 7: Review and consolidation

Program overview and recap, and an outline of next steps to take. Advise on follow-up questionnaires for longitudinal follow-up, and link to forums for further engagement (aimed at enhancing retention).

Standard-Care Group (MS Online standard-care course):

Structure and mode of delivery:

The standard-care course will be structured and delivered in the same way as the intervention course. That is, the total length of course is six weeks (7 sessions, 2 sessions per week with 2 weeks of catch-up).

Content:

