Data interpretations from interviews one month after completing the MS Online course and 12 months after completing the MS Online course will be performed individually at each time-point. Comparisons between data interpretations at the different time intervals will also be performed.

Student participation:

This protocol may be used towards a student PhD project in the future but at present, no student has been assigned to work on this research project.

Table 1: Summary of RCT time frame

Assessment/Measure	No. Questions	Timeframe							
		Screening	Baseline	Complete Online course	One month after Online course	6 months after Online course	12 months after Online course	2.5 years after Online course	
Informed consent	1		X						
Age	1	X	X						
MS type diagnosed	2	X	X			X	X	X	
MS duration	2	X	X			X	X	X	
Do you follow a MS-specific lifestyle program?	2	X	X			X	X	X	
Do you follow a MS-specific diet	2	X	X			X	X	X	
Sex and gender	2		X						
Residential address and country	1		X					X	
Country of birth	1		X						
Height/weight	2		X			X	X	X	
Comorbidities	2		X			X	X	X	
Marital status	1		X			X	X	X	
Education	1		X						
Employment status	1		X			X	X	X	
Alcohol and smoking	4		X			X	X	X	
Medications	4		X			X	X	X	
Perceived Social Support	12		X			X	X	X	
Lifestyle factors									
Physical activity: IPAQ-SF	7		X			X	X	X	
Meditation: MAQ	3		X			X	X	X	
Sun exposure	4		X			X	X	X	
Diet quality: DHQ	21		X			X	X	X	
Omega-3 intake: dose, frequency	3		X			X	X	X	

Vitamin D intake: dose, frequency	3	X		X	X	X
Health outcomes						
HRQOL: MSQOL-54	54	X		X	X	X
Disability: PDDS	1	X		X	X	X
Anxiety and depression: HADS	14	X		X	X	X
Fatigue: FSS	9	X		X	X	X
Self-efficacy: UWSE-6	6	X		X	X	X
Qualitative interviewing	(7)		X		X	

If clinically significant improvement in HRQOL subset scores in Intervention group from baseline, we will consider an amendment to the RCT to provide participants in the standard-care access to the intervention course

X

If no clinically significant improvement in HRQOL subset scores in Intervention group from baseline, the RCT will not be amended

X

Total no. quantitative data questions (not including qualitative)	5	166		159	166	160
---	---	-----	--	-----	-----	-----

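### Section 5.3(c) defines binge drinking by a weekly total, which cannot identify a heavy-drinking occasion; the BMI formula in the same section is also misprinted

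*Combined protocol and SAP*

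**What the plan says.** Section 5.3 lists alcohol among the lifestyle and behaviour outcomes measured at baseline, 6 months, 12 months and 2.5 years. Item (c) opens with "Volume and frequency of alcohol consumed will be queried" and gives the unit: "In Australia a standard drink is considered to be 10 grams of ethanol". It then adds the frequency of binge drinking, attributed to a national statistics bureau and defined "as more than 7 drinks a week for men, and more than 5 for women, will be queried". No other section gives a per-occasion or per-day measure. Item (b) says that the alcohol question of the diet questionnaire was replaced by another alcohol measure, and item (c) is the only alcohol measure described.

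Section 5.2 aims to compare adoption of and adherence to lifestyle change between the arms. Section 6.1 says of Session 6: "This session will cover risks associated with smoking and excessive alcohol intake and MS progression". The standard-care course uses the same seven modules.

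Under the other measures in section 5.3, item (d) states: "Body Mass Index (weight/height)² will be calculated from data collected on self-reported participant weight and height". The result is then to be classified by the WHO system and compared with baseline.

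**The concern.** The frequency of a binge is a count of episodes, whereas the threshold given is a total over a week. The two do not fit together. People with the same weekly total can have very different drinking patterns, and the definition treats them alike. It can therefore misclassify in both directions: modest drinking spread over the week is counted as bingeing, and a single heavy session can go uncounted.

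What is at stake is one lifestyle outcome. If the intervention changed episodic heavy drinking without much change in weekly volume, or the reverse, this variable could not tell the two apart. It would mostly repeat what the volume and frequency items already provide.

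The BMI formula is a smaller matter in the same section. With the exponent outside the bracket, weight is squared as well as height, and the values no longer relate to any BMI classification.

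**Working it through.** The plan states no computed figure for either item, so there is nothing to reproduce. The check applies the written rules to simple cases.

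**Binge rule.** Inputs from section 5.3(c): men more than 7 drinks a week, women more than 5 (reading the weekly unit as carrying over), and 10 g of ethanol per drink. The drinking patterns are illustrative.

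| Pattern over one week | Total | Largest day | Man classed as binger (>7) | Woman classed as binger (>5) |
|---|---|---|---|---|
| 1 drink on each of 6 days | 6 | 1 | no | yes |
| 1 drink on each of 7 days | 7 | 1 | no | yes |
| 2 drinks on one day, 1 on each of six | 8 | 2 | yes | yes |
| 4 drinks on each of 2 days | 8 | 4 | yes | yes |
| 8 drinks on 1 day | 8 | 8 | yes | yes |
| 7 drinks on 1 day, none otherwise | 7 | 7 | no | yes |
| 5 drinks on 1 day, none otherwise | 5 | 5 | no | no |

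The lowest whole-drink totals that cross the threshold, as daily averages, are:
- women: 6/7 = 0.86 drinks a day, or 60/7 = 8.6 g of ethanol;
- men: 8/7 = 1.14 drinks a day, or 80/7 = 11.4 g of ethanol.

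The three patterns that total 8 have largest days of 2, 4 and 8 drinks but receive the same classification. The number of heavy occasions therefore cannot be recovered from the weekly threshold.

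**BMI.** The formula as printed is (w/h)²; the usual formula is w/h². Their ratio is w, so with kg and m the printed formula is too large by a factor equal to the weight in kg. Body sizes are assumed.

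| Weight, height | (w/h)² | w/h² |
|---|---|---|
| 45 kg, 1.50 m | 900 | 20.0 |
| 70 kg, 1.75 m | 1600 | 22.9 |
| 90 kg, 1.80 m | 2500 | 27.8 |
| 120 kg, 1.90 m | 3989 | 33.2 |

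With height in cm the printed formula gives 0.09 for the first row and 0.40 for the last. Neither scale yields a possible BMI.

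**The case against.** The strongest reply concerns weight in the trial. The primary outcomes are the two MSQOL-54 composites, and the secondary outcomes are depression, anxiety, fatigue, disability and self-efficacy. Section 9.3 names no alcohol or BMI analysis. The adherence domains listed in section 6.1 omit alcohol, Table 1 places "Alcohol and smoking" outside its lifestyle block, and BMI is filed under other measures. No objective mentions episodic heavy drinking, and volume and frequency already speak to excessive intake. All of this stands, and it limits the point to one lifestyle variable and one formula.

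A second reply is that the survey is an attachment not reproduced here, so the fielded question may be worded per occasion, and that the definition is credited to an outside source that cannot be checked. That stands as uncertainty, but it does not remove the need for a correction. If the survey follows the protocol, the variable is defective; if it does not, the protocol misdescribes its own outcome. It is also fair that the number of weeks above the threshold could be asked. That would be a valid count, but of weeks and not of heavy-drinking occasions.

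On BMI, the exponent may be a typing or text-extraction slip, and an analyst would probably compute kg/m² anyway. This is likely, which is why it is only a formula correction.

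A reader might infer two further things that the documents do not support:
- **Too few questions in Table 1.** It allots 4 questions to alcohol and smoking, fewer than the variables named in section 5.3. But smoking follow-ups depend on smoking status, items may have several parts, and the survey is not shown. A shortfall is not demonstrated.
- **BMI comparison with baseline carries no information.** With adult height fixed, (w/h)² rises with weight, so the direction of each person's change survives even under the printed formula. Only the classification fails.

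**Conclusion.** The point holds for the binge item as written. A weekly threshold does not measure binge frequency, and it misclassifies in both directions: women from 6 and men from 8 drinks a week count as bingers however the drinks are spread, while 5 (women) or 7 (men) in one sitting with none otherwise does not count. A reader might take this to mean that anyone drinking once a day is labelled a binger. That is true only for women, because a man at exactly 7 a week is not above 7.

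The consequence is that one listed lifestyle outcome largely duplicates weekly volume and cannot show a change in episodic heavy drinking. The primary and secondary endpoints and the sample size are not touched. How many participants would be misclassified cannot be estimated, since the documents give no drinking data.

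The BMI formula is wrong as printed and makes the WHO classification meaningless if followed. It is probably clerical.

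The conclusion assumes that the weekly unit applies to both sexes and that the survey follows section 5.3. It does not depend on what the cited bureau's definition says.

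**What to change.** Restate the binge item in section 5.3(c) as the number of occasions, in a stated recall period, on which the participant had more than a sex-specific number of 10 g drinks. Take that number from a per-occasion definition checked against the cited source, and make the protocol and the fielded survey agree. Show the 10 g drink on the form, since recruitment covers at least five countries. Derive the weekly total from the volume and frequency items, and report it under its own name.

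In section 5.3(d), write BMI as weight in kg divided by the square of height in m.

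The cost is one reworded item and one formula edit. The drawback is possible loss of comparability with any earlier data collected under the weekly wording. The documents describe no such data, but the investigators should check. If baseline answers have already been collected, keep them as a weekly-volume measure and do not label them as binge frequency.

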6. STUDY DESIGN

6.1 STUDY TYPE & DESIGN & SCHEDULE

1. Study Type: Clinical trial

Randomised controlled trial, involving:

- a. Epidemiological analysis of quantitative data
- b. Qualitative analysis of semi-structured interviews

2. Study Design (refer to Table 1)

- I. This is a single-site study that will be conducted at the Neuroepidemiology Unit in the Centre for Epidemiology and Biostatistics, Melbourne School of Population and Global Health at The University of Melbourne, involving online recruitment of participants with MS from Australia, New Zealand, USA, UK and Canada. The decision was made to make this a single-site study to guarantee that all data collected from participants (both personal participant data and responses to self-reported questionnaires) will be safely and securely stored in one location (on the University of Melbourne server).
- II. For participant recruitment, details of the RCT will be published on MS society websites and social media sites throughout Australia, New Zealand, USA, UK and Canada seeking interested people with MS to participate in the MSOC - RCT.
- III. Interested participants (people with relapsing-remitting MS) will be asked to click on a link on the notice advertising the MSOC - RCT which will direct them to 7 eligibility questions related to: (1) their age; (2) the type of MS they were diagnosed with; (3) the year they were diagnosed with MS (4,5) whether they follow a MS-specific diet and if so, the diet they follow (6,7) whether they follow a MS-specific program and if so, the program they follow.

- IV. Participants with MS over the age of 18 fulfilling inclusion and exclusion criteria from Australia, New Zealand, USA, UK, Canada and other countries who read, write and speak English will be invited to participate in the study. Note, the recruitment period will be up to two months from the date of the first participant recruitment or earlier, if the required number of eligible participants have been recruited.
- V. Interested participants meeting the study eligibility criteria (Refer to Section 6.2 and 6.3 for eligibility criteria) after completing the eligibility questions will be emailed a participant information form and consent form. Once participants have provided their consent by ticking a box online, participants will be emailed a link to the baseline questionnaire to obtain demographic data and obtain data on lifestyle and outcome measures (Section 4.3, Table 1). Interested participants not meeting the study eligibility criteria will be excluded and notified by email that they were not eligible to participate in the study and thanking them for their interest.
- VI. Participants will be randomised to either the MS Online intervention course or the MS Online standard-care course at a ratio of 1:1 using simple randomisation. Randomisation will occur over a 2-week period after recruitment of eligible participants.
- VII. Participants will undertake the MS Online course (intervention arm or standard-care arm) over a 6-week period. Note, each arm is of comparable length and content-type (video, interviews, images, interactivity), to minimise variability in 'dose' received between intervention and standard-care groups. Both courses will follow a similar structure throughout, limiting differences in how the content of the course is presented.
- VIII. Patient-reported outcomes measures (Section 4.3, Table 1) will be determined after a period of 6 months, 12 months and 2.5 years after the completion of the MS Online course. This will involve participants from the MS Online intervention arm and the MS Online standard-care arm completing validated questionnaires online (following instructions and reminders, if necessary, from study team members). These measures will determine participants adherence to lifestyle recommendations of the Online intervention and standard course with respect to diet, exercise, omega 3 intake, vitamin D intake, meditation and sun exposure (Table 1). Health outcomes related to participant's quality of life, depression, anxiety, fatigue, disability and self-efficacy.
- IX. The primary objective of the study will be assessed at the 12-month and 2.5 year follow-up. That is, Health-related quality of life (HRQOL) calculations for Physical Health Composite

(PHC) and Mental Health Composite (MHC) scores derived from the MSQOL-54 for participants in the intervention and standard-care arm will be calculated in the intervention and standard-care arms.

We will consider amending the RCT protocol to allow participants in the standard-care arm access to the MS Online intervention course before the end of the study (ie before the 2.5-year follow-up) in the event:

- a) clinically significant increases in either the PHC and MHC scores of MSQOL-54 (≥ 5) (Osoba et al., 1998; Taphoorn & Bottomley, 2005) from baseline are found in participants in the intervention arm at the 12-month follow-up who are *adhering to lifestyle recommendations* of the Online Lifestyle modifications course, but
- b) clinically significant improvements in either PHC or MHC are not found in participants in the standard-care arm at the 12-month follow-up.

If clinically significant improvements in either the PHC and MHC scores of MSQOL-54 are not found between baseline and 12 months in participants in the intervention arm *adhering to lifestyle recommendations* of the MS Online intervention course, the RCT will continue to as described to the 2.5 year follow-up.

If there are no amendments to the study, all participants will be notified of the study arm they were allocated to at the completion of the study. All participants in the standard-care arm will be provided with a link to access the MS Online intervention course.

- X. Qualitative interviewing consisting of semi-structured interviews by trained qualitative interviewers will be conducted on a randomly selected subset of participants (approximately 15 participants from intervention and standard-care arms, respectively) will be performed within 1 month of and 12 months after completing the MS Online course.
- XI. During enrolment in the trial, participants in both arms of the RCT will be advised to continue with normal medical treatment with their existing neurologists and healthcare providers and to continue with their usual medications, as recommended by their physicians.

Intervention group (MS Online intervention course):

Structure of delivery

In a seven-module, seven-session, self-administered program, participants in the intervention arm would be presented with an integrated lifestyle modification program including information and

support regarding each of the key lifestyle modifications. Modules will be released on a timed-schedule, twice per week, with future modules gated until completion of preceding modules, but previous modules available for review throughout the entire intervention period. The total length of course is six weeks (7 sessions, 2 sessions per week with 2 weeks added on to the end for catch-up), specified by participants in the MSOC – feasibility study to be of suitable length. The course remains open for a total of six weeks to enable participants to complete the course.

Mode of delivery

Delivery of the lifestyle intervention will be via invitation-only, online course. Participants will be required to complete each module within specified six weeks of the course. There is no time limit set for the completion of each module; however, the next module cannot be accessed until the previous module is complete, and all must be completed by the end of the intervention period for participant to be considered a ‘completer’. Modules are composed of video content, written content, interactive (non-assessed) content, and non-hurdle assessments. Participants are required to self-navigate modules with technical support provided only to address functionality issues within the software.

Content

The integrated lifestyle modification program translates the research evidence regarding modification of lifestyle related risk factors and health outcomes based on a detailed review of the literature around modifiable lifestyle risk factors that may influence MS disease progression, as outlined in the book *Overcoming Multiple Sclerosis: the 7-step recovery program* (Jelinek, 2016).

The MS Online Course also contains a community forum. Links to articles and other prompts will encourage participants to contribute their thoughts. A researcher will be delegated to oversee the forum to moderate the forum to facilitate participant engagement and ensure appropriateness of content.

Session 1: Introduction to the Program and participants

Welcome to the course and overview of MS (medical definition). How to study the course; introduction to the web-based intervention: how to proceed, how to navigate, what to expect and to outline the endpoints for participants. Validating Overcoming MS program → providing previous research/evidence on efficacy.

Session 2: Diet

Evidence behind a dietary influence on MS disease activity and QOL: evidence on saturated fat, and evidence regarding diet and its relationships with MS onset and progression. Introduction to dietary plan and benefits of different food groups.

Session 3: Sunlight and vitamin D

Detailed background information about how vitamin D is made from the action of sunlight is presented, along with evidence supporting a role of vitamin D in MS disease activity. Recommendations for optimal levels of supplementation and blood levels are presented.

Session 4: Physical activity/Exercise

The benefits of exercise are explained for people with MS (neurological, cognitive, physical), how and why. In addition, evidence regarding the benefits of exercise will be presented. How to implement an exercise plan with video examples provided.

Session 5: Stress and stress reduction

Introduction to mental health and relevance in MS. Participants are introduced to the science behind stress and its link to inflammation/MS. Mind-body connection, meditation and other stress reduction techniques to supplement the practical sessions on meditation they receive throughout the program. How to develop a mental health and wellbeing improvement strategy.

Session 6: Family primary prevention

Participants are introduced to the issue of primary prevention of MS in close family members who are at increased risk of developing the disease, and strategies for reducing this risk. This session will cover risks associated with smoking and excessive alcohol intake and MS progression.

Session 7: Review and consolidation

Program overview and recap, and an outline of next steps to take. Advise on follow-up questionnaires for longitudinal follow-up, and link to forums for further engagement (aimed at enhancing retention).

Standard-Care Group (MS Online standard-care course):

Structure and mode of delivery:

The standard-care course will be structured and delivered in the same way as the intervention course. That is, the total length of course is six weeks (7 sessions, 2 sessions per week with 2 weeks of catch-up).

Content:

The content of the standard-care course will be delivered in the same seven modules as the intervention course (as above). The standard-care course will be populated with information collected from a multitude of MS society websites from around the world, such as MS Australia, MS Research Australia and The National MS Society (United States); text, video and image/animation content has been compiled into modules to mirror the intervention course's modules. The standard-care course aims to reproduce the advice that people with MS typically receive during medical consultations and online advice from MS Societies.

A separate community forum is available as part of the standard-care course specifically for standard-care participants.

MS Online Intervention course group and MS Online Standard-care course group:**Data collection, management and analysis:*****Quantitative data***

Quantitative data will be collected via validated self-reported questionnaires completed by participants at specified time points (Table 1).

Para data (administrative data such as number of participant logins, etc) will be collected via Google Analytics and functionality integrated into the WordPress platform. Google Analytics provides data tracking on how participants interact with the online course, such as average time per page, what interactive elements participants are engaging with, what pages people commonly exit the course on, and many others. The analytics integrated into the platform itself will allow us to analyse the number of participants that drop-out over the length of the course, and when they do so.

Data will be stored in a re-identifiable format as described in Section 10.

Quantitative data collection feasibility

As assessed by the qualitative component of the MSOC – Feasibility study, participants indicated that the MS Online course over six weeks with two sessions every week was feasible to complete. Importantly, participants have the option to complete the MS Online course at a time and location that is convenient to them.

The complete patient-reported questionnaire with approximately 150 questions has been found to take approximately 60 minutes to complete. Participants will be able to login and complete this questionnaire over time. The participants will be requested to complete this questionnaire on four separate occasions (baseline, 6 months, 12 months and 2.5 years) and due to previous studies that we have performed within the Neuroepidemiology Unit utilising questionnaires of a similar length over 7.5 years ((Marck et al., 2018; Weiland et al., 2018), we do not believe the questionnaire will create an unacceptable burden on participants.

Quantitative data analysis:

We will measure adherence to lifestyle modification recommendations in people with MS enrolled in the MS Online intervention and the MS Online standard-care arm (control) using validated patient-reported questionnaires.

We will examine and compare clinical and health outcomes of depression, anxiety, fatigue, disability, self-efficacy and quality of life in people with MS in the short-term (6 months and 12 months) and medium-term (2.5 years) in people enrolled in the MS Online Intervention course arm and people enrolled in the MS Online standard-care course arm.

Statistical analyses will enable us to examine whether a causal relationship exists between lifestyle factors and clinical and health outcomes in people with MS. These analyses are anticipated to be completed within 6-12 months of collecting data for short-term and long-term analyses, respectively.

Qualitative data:

Qualitative data will comprise edited transcripts of recordings from semi-structured interviews from 15 randomly selected participants from the intervention arm and the standard-care arm carried out within one month of completing the MS Online course and 12 months after completing the MS Online course (the same people will be interviewed at both time points).

Interviews will be digitally recorded and transcribed by voice recognition software. Data will be stored in a re-identifiable format and encrypted files will be securely stored as described in Section 10.

Qualitative data collection feasibility:

The qualitative component of the MSOC – RCT is similar to the qualitative component of the MSOC – Feasibility study we performed. This interviewing technique was found to be both effective and participants reported positive feedback following interviews.

Qualitative data analysis:

